10.2 Sample Size Considerations

Serum glucose values after a carbohydrate load have significant intra-individual variation, if done on the same person but at a different time the results can vary up to 16.7% (21) The two tests will be considered equivalent if the difference between them is less than or equal to 20%. For a mean one hour (+/- 15 minutes) post 75g carbohydrate load serum blood glucose of 10.6 mmol/L (standard deviation of 1.78 mmol/L) a sample of 28 will provide 80% power at alpha of 0.05 for a test of equivalence with Dex4® tablets assuming a 20% margin of equivalence. The sample size calculation was carried out using PASS Version 12 (Hintze, J. (2014). NCSS, LLC. Kaysville, Utah.) Accounting for loss to follow up of 33%, 42 women will need to be recruited, respectively. Based on data from Alberta, 20% of women screen positive on an 50g GCT (22). Approximately 230 women deliver at Sunnybrook every month, of those 45 will screen positive on the GCT. Assuming a 20% successful recruitment rate we should be able to complete recruitment in 4-6 months.

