	APPENDICES	30
	APPENDIX A: SCHEDULE OF EVENTS	31

LIST OF ABBREVIATIONS

The following abbreviations describe terms, documents and study personnel used in the conduct of this study protocol.

AE	Adverse Event/Adverse Experience
CC	Coordinating Centre
CIOMS	Council for international Organizations of Medical Sciences
CRF	Case Report Form
CCTS	Centre for Clinical Trial Support
EC	Ethics Committee
ICH	International Conference on Harmonisation
IP	Investigational Product
pCRF	Paper Case Report Form
GCP	Good Clinical Practice
ICF	Informed Consent Form
PHI	Personal Health Information
PI	Principal Investigator
PM	Product Monograph
QI	Qualified Investigator
REB	Research Ethics Board
RCT	Randomized Controlled Trial
SAE	Serious Adverse Event/Serious Adverse Experience
SOP	Standard Operating Procedure
SRI	Sunnybrook Research Institute
SUADR	Serious and Unexpected Adverse Drug Reaction
TMF	Trial Master File

PROTOCOL SUMMARY

Protocol Title (Short Title)	DIAgnosing GDM usiNg Oral Sugar InStead (DIAGNOSIS)
	Randomized crossover study comparing the standard glucose beverage and Dex4® tablets for 2 hour oral glucose tolerance testing in pregnant women with a positive screen on the 50g glucose tolerance challenge for gestational diabetes
Protocol Number	Assigned REB number 418-2018.
Phase	II
Study Design	Phase II randomized controlled crossover study
Study Duration	6 months
Setting	Single-centre
Sample Size	28 required by power calculation, aiming to recruit 42 (accounting for 33% loss)
Main Inclusion Criteria	
 • Positive 50g GCT result between 7.8-11.0 mmol/L • singleton pregnancy
Primary Outcome(s):	2 hour serum glucose value after the carbohydrate challenge. The study is powered to assess equivalence between Dex4® tablets and 75g of glucose beverage.
Secondary Outcome(s):	Side effects associated with Dex4® tablets and participant preference of using Dex4® tablets or the standard glucose beverage for OGTT testing.
Investigational Product (IP) and Planned Use	The investigational product to be used is (Dex4®) dextrose monohydrate tablets, containing 4g of dextrose monohydrate per tablet equivalent to 3.64g of dextrose anhydrous. After a minimum 8 hour fast, 21 Dex4® tablets will be ingested over the span of 5 minutes. Venous blood sampling for serum glucose will be taken prior to ingestion , and 1 and 2 hours (+/- 15 minutes) after ingesting the Dex4® tablets.

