4 STUDY DESIGN

4.1 General Design

Our project is a population-based, prospective randomized crossover study. Women who fall into the screen positive group of the 50g GCT (1 hour serum glucose of 7.8-11 mmol/L) will be offered participation in the study. 28 Participants will be recruited and will be randomly assigned using a pre-populated allocation table to take either the standard OGTT test (75g of glucose beverage) first or the alternative OGTT test (21 Dex4® tablets) first. The first test will be referred to as OGTT-1 and the second test will be referred to as OGTT-2. After completing OGTT-1 at the first test appointment, a questionnaire about pregnancy, health, diet and exercise habits, and side effects from the first test will be completed by the participant (Questionnaire A). After completing OGTT-2 at their second test appointment, a questionnaire about side effects from the second test and test preference will be completed by the participant (Questionnaire B). Each woman will complete both tests within one week and each subject will serve as their own control. Results will be kept blinded in the case report forms until both OGTT tests are done. Serum glucose will be measured using the same internationally standardised glucose-oxidase method (RocheDiagnosis) in the Sunnybrook Biochemistry lab. After serum glucose measurement, all results will be sent to the research team but only the standard of care glucose beverage test data will appear in electronic (or classical) medical records and be used for GDM diagnosis.

The following data will be collected by questionnaire at the first OGTT appointment:

- Estimated date of delivery
- # of previous pregnancies
- Previous diagnosis of GDM
- Pre-pregnancy weight (kg);
- Height (cm);
- Ethnic group (Caucasian, Indigenous, Hispanic, South Asian, East Asian, African, Middle Eastern, Other)
- History of macrosomic infant - ≥ 4000 g
- Polycystic ovary syndrome (yes-no);
- Medication (for corticosteroid use);
- First degree family history of T2DM
- Length of fast (hrs)
- Side effects (nausea, vomiting, headache, dizziness, sweating, other)

The following data will be collected by questionnaire at the second OGTT appointment:

- Side effects
- Preference for Dex4® or glucose beverage

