4.2 Primary Outcomes/Endpoint(s)

The primary outcome measures are fasting 1hr and 2hr PG levels from the Dex4® and glucose beverage OGTTs. Serum glucose values after a carbohydrate load have significant intra-individual variation, if done on the same person but at a different time the results can vary up to 16.7% (21) The two tests will be considered equivalent if the difference between them is less than or equal to 20%.

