10.4 Final Analysis Plan

Serum glucose values after a carbohydrate load have significant intra-individual variation, if done on the same person but at a different time the results can vary up to 16.7% (21) The two tests will be considered equivalent if the difference between them is less than or equal to 20%. For a mean one hour post 75g carbohydrate load serum blood glucose of 10.6 mmol/L (standard deviation of 1.78 mmol/L) a sample of 28 will provide 80% power at alpha of 0.05 for a test of equivalence with Dex4® tablets assuming a 20% margin of equivalence. The sample size calculation was carried out using PASS Version 12 (Hintze, J. (2014). NCSS, LLC. Kaysville, Utah.) Accounting for loss to follow up of 33%, 42 women will need to be recruited, respectively.

To evaluate equivalence, the mean of the differences at each time point (fasting, 1 hr and 2 hrs after glucose beverage/Dex4® tablets) will be calculated and a two-sample equivalence-test will be used to compare the means. Based on previous reports of intra-individual variation in 2 hour OGTT of 16.7% for blood glucose measurement (21), Dex4® tablets will be considered equivalent to glucose beverage if the equivalence margin is less than or equal to 20%.

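### The 80% power stated for 28 women does not follow from the 1-hour inputs in this crossover, and the 2-hour value that the Summary names as primary has no calculation

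*Protocol*

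**What the plan says.** - **Sample size (10.2, repeated in 10.4).** From a 1-hour mean of 10.6 mmol/L, an SD of 1.78 mmol/L and a 20% margin, the protocol concludes that "a sample of 28 will provide 80% power at alpha of 0.05 for a test of equivalence with Dex4® tablets". Section 5 repeats the figure without the mean, the SD or the time point. Allowing for 33% loss, 42 are to be recruited.
- **Design (4.1).** The study is a randomized crossover: "Each woman will complete both tests within one week and each subject will serve as their own control".
- **Analysis (10.4 and Summary).** The mean of the differences is calculated at each of the three time points, and then "a two-sample equivalence-test will be used to compare the means".
- **Primary outcome.** The Summary gives "2 hour serum glucose value after the carbohydrate challenge" and continues directly: "The study is powered to assess equivalence between Dex4® tablets and 75g of glucose beverage". Section 4.2 differs: "The primary outcome measures are fasting 1hr and 2hr PG levels".
- **2-hour variability.** The only figure is in 10.4 and the Summary, which justify the margin by "intra-individual variation in 2 hour OGTT of 16.7% for blood glucose measurement".

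**The concern.** The power statement is the only justification given for the sample size. A paired equivalence calculation needs the SD of the within-woman difference (or a single-measurement SD plus a correlation), the true difference assumed, and the alpha for each one-sided test. The protocol gives one SD of unspecified type and an alpha not assigned per side, with no correlation and no true difference. A reader therefore cannot tell what the 80% means or how large a real difference between the products it allows for.

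The sizing is also done at 1 hour, while the Summary attaches its claim of power to the 2-hour value. A percentage margin shrinks in mmol/L as the mean falls, so a 1-hour result does not carry over to 2 hours without a 2-hour mean and SD. Finally, a two-sample comparison of means does not match a design in which each woman is her own control.

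**Working it through.** **Inputs from the protocol.** N = 28, alpha 0.05, mean 10.6, SD 1.78, margin 0.20 × 10.6 = 2.12 mmol/L (10.2); each woman takes both tests (4.1).

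**Assumptions, because the protocol is silent.** True difference 0; alpha 0.05 or 0.025 per one-sided test; within-woman correlation ρ of 0, 0.3 or 0.5; 1.78 is the SD of a single measurement. If 1.78 were the SD of the paired difference, the result is the ρ = 0.5 row.

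**Method.** Two one-sided t tests (TOST), with power integrated over the sampling distribution of the variance. SD of the difference = 1.78 × √(2(1 − ρ)).

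**1. Attempt to reproduce 80% with 28 pairs at 1 hour**

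| ρ | SD of difference | Power, 0.05 / 0.025 per side | Pairs needed for 80% | True difference at which 28 pairs give 80% |
|---|---|---|---|---|
| 0 | 2.517 | 99.3% / 98.0% | 14 / 17 | 8.55% / 7.0% |
| 0.3 | 2.106 | 99.96% / 99.8% | 10 / 13 | 10.4% / 9.1% |
| 0.5 | 1.780 | over 99.99% / over 99.99% | 8 / 10 | 11.9% / 10.8% |

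Fitting a period effect (26 df) leaves the ρ = 0 row at 99.3% / 98.0%. With no true difference, 80% would need an SD of the difference of 3.74 at 0.05 per side. That exceeds the largest value an SD of 1.78 permits (2 × 1.78 = 3.56). At 0.025 per side it would need 3.34, which is ρ of about −0.76.

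**2. Readings that do not use the pairing**

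- 28 values per product, treated as two independent samples: 99.4% / 98.4%.
- 28 as the total of a parallel two-group trial, 14 per group: 84.5% / 71.7%.
- 13 per group (26 in total): 80.8% at 0.05 per side. 16 per group (32 in total): 80.6% at 0.025.
- 14 per group reaches exactly 80% at 0.05 per side with a true difference of about 3.1%.

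The parallel-group reading comes nearest to the stated pair of 28 and 80%, but it does not match exactly and it is not this design.

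**3. The 42.** 28 / (1 − 0.33) = 41.8, so 42 reproduces.

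**4. The 2-hour value.** No 2-hour mean or SD is given, so only conditional figures are possible, all with no true difference and 28 pairs.

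- If the 16.7% is read as a within-woman coefficient of variation (assumption), the SD of the difference is 0.167 × √2 = 0.236 of the mean. Power is 99.3% / 98.2% whatever the mean.
- If the 2-hour mean is lower and the absolute SD stays at 1.78 (assumption), power falls. At an illustrative mean of 8 mmol/L the margin is 1.60, and power is 89.7% / 80.0% at ρ = 0 and 97.7% / 94.4% at ρ = 0.3.
- Across illustrative means of 7 to 9 the lowest result is 61.9%. It needs mean 7, ρ = 0 and 0.025 per side together. At ρ = 0.3 or more no result in that range is below 84.7%.

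**The case against.** **The figure may be right for inputs that are not shown.** Planning for a non-zero true difference is ordinary practice, and a value of roughly 7% to 12% entered in the software would give 80% with 28 pairs. This stands as a possible explanation. It does not rescue the statement, because that value determines what the 80% means and the protocol omits it.

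**The named test is two-sample, so 28 may be a two-group total.** This is also plausible: 26 in total gives 80.8% at 0.05 per side, and 28 gives 84.5%. If so, the sizing ignored the crossover, which is a reason to correct it. A kinder reading is that two-sample means comparing within-woman differences between the two sequence groups, a proper crossover analysis. Power is then still 99.3% / 98.0%, and the wording should say so.

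**Nothing is lost at 1 hour.** Agreed. If the true difference is small, 28 completers are more than enough, and the discrepancy does not inflate type I error.

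**The 2-hour worry rests on assumptions.** Largely true. Zero correlation sits poorly with women serving as their own controls, and the protocol's only 2-hour variability figure, read as a within-woman coefficient of variation, gives 98% to 99%. A reader might infer that the trial is underpowered for its primary outcome; the protocol does not support that. It shows only that power at 2 hours has not been calculated.

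**Conclusion.** The point holds in this form. The 80% at 28 women is not obtained from the stated 1-hour inputs in this crossover. With no true difference the same inputs give at least 98.0% at any non-negative correlation, for either choice of alpha per side. Sizing as a parallel trial and an unstated true difference are both possible origins, and the protocol does not allow a choice between them. A reader might infer that one specific wrong input has been identified; it has not.

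The 1-hour part alone is a reporting correction. The part with possible consequence is the time point. The Summary's primary outcome is the 2-hour value, section 4.2 lists three time points, and only 1 hour is sized. Power at 2 hours is unsupported: about 98% to 99% if the 16.7% is a within-woman coefficient of variation, lower if the 2-hour mean is lower with a similar absolute SD. Both are assumptions. The change should be made, but no lack of power has been shown.

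**What to change.** 1. Reconcile the primary time point between the Summary and 4.2. If all three time points stay primary and all must show equivalence, state the joint power.
2. Redo the calculation in 10.2 and 10.4 for the chosen time point as a paired or crossover TOST. State its mean, the SD of the within-woman difference (or a single-measurement SD with the correlation), the true difference assumed and the alpha per one-sided test. Restate the power that 28 completers give for the 20% margin, and carry it into section 5.
3. In the Summary and 10.4, replace the two-sample test with the matching paired or crossover TOST, so that sizing and analysis agree.
4. Editorial only: 4.1 says "28 Participants will be recruited and will be randomly assigned" and 2.3 also describes 28 women, while the Summary, 5, 10.2 and 10.4 recruit 42 to keep 28. Make clear in 2.3 and 4.1 that 28 means completers.

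The cost is one recalculation and text edits. The correction itself asks for no extra patients, but the 2-hour power has to be calculated before 28 can be called sufficient for that outcome.

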10.3 Stopping Rules

This study will be stopped prior to its completion if: (1) the intervention is associated with adverse events that call into question the safety of the intervention; (2) difficulty in study recruitment or retention will significantly impact the ability to evaluate the study endpoints; (3) any new information becomes available during the trial that necessitates stopping the trial; or (4) other situations occur that might warrant stopping the trial.

10.4 Final Analysis Plan

Serum glucose values after a carbohydrate load have significant intra-individual variation, if done on the same person but at a different time the results can vary up to 16.7% (21) The two tests will be considered equivalent if the difference between them is less than or equal to 20%. For a mean one hour post 75g carbohydrate load serum blood glucose of 10.6 mmol/L (standard deviation of 1.78 mmol/L) a sample of 28 will provide 80% power at alpha of 0.05 for a test of equivalence with Dex4® tablets assuming a 20% margin of equivalence. The sample size calculation was carried out using PASS Version 12 (Hintze, J. (2014). NCSS, LLC. Kaysville, Utah.) Accounting for loss to follow up of 33%, 42 women will need to be recruited, respectively.

To evaluate equivalence, the mean of the differences at each time point (fasting, 1 hr and 2 hrs after glucose beverage/Dex4® tablets) will be calculated and a two-sample equivalence-test will be used to compare the means. Based on previous reports of intra-individual variation in 2 hour OGTT of 16.7% for blood glucose measurement (21), Dex4® tablets will be considered equivalent to glucose beverage if the equivalence margin is less than or equal to 20%.

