5.3 Participant Recruitment

After women receive a positive 50g GCT result, they are contacted by their obstetrical provider and advised to complete a 75g OGTT. At this point they will be informed of the study and offered for the study staff to contact the patient to discuss the trial in more detail. Obstetrical offices will also have recruitment posters and brochures offering women to contact the trial team directly. If the woman agrees to participate, informed consent will be obtained prior to participation. Women will be considered enrolled in the study upon signing of the informed consent form

5.3.1 *Randomization Procedures (if applicable)*

Participants in this study will be randomly assigned using a pre-populated allocation table produced by the study's biostatistician to take either the standard OGTT test (75g of glucose beverage) first or the alternative OGTT test (21 Dex4® tablets) first.

5.3.2 *Blinding and Unblinding Procedures (if applicable)*

The study treatment is not blinded.

The results of the Dex4® OGTT will not be considered clinically relevant and will not be disclosed to the participant and the obstetrical care team. The results of the standard OGTT will be released to the obstetrical care team upon completion so that patients' standard clinical care is not delayed.

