6.2 Behavioral Intervention(s) Description (if applicable)

During the time between the two OGTT tests, participants will be asked to refrain from drinking alcohol, and performing nonroutine exercise.

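### Section 10.4 compares the products without a period or sequence term although test order is randomised, so unequal evaluable sequences bias the difference, modestly unless loss depends on order

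*Protocol*

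**What the plan says.** Section 4.1 describes the design: "Our project is a population-based, prospective randomized crossover study". Under Section 5.3.1 women are "randomly assigned using a pre-populated allocation table produced by the study's biostatistician to take either the standard OGTT test" first or the tablet test first. The allocation ratio and any blocking are not stated. Section 4.1 adds: "Each woman will complete both tests within one week and each subject will serve as their own control".

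Section 10.4 then fixes the analysis. The estimate is "the mean of the differences at each time point"; the samples concerned are the fasting, one-hour and two-hour draws for each product. On the test itself, the section states: "a two-sample equivalence-test will be used to compare the means". The Statistical Analysis row of the Protocol Summary says the same. Neither place mentions period, sequence or order, and neither says what the two samples are.

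Three other parts of the protocol bear on the point:
- Section 6.2: "During the time between the two OGTT tests, participants will be asked to refrain from drinking alcohol, and performing nonroutine exercise".
- Section 10.2 plans for 33% loss, from 42 recruited to 28.
- Section 5 encourages women who withdraw to complete the beverage test, and Section 5.3.2 releases the beverage result as soon as that test is done. Sections 4.1 and 6.1.3 instead hold results back until both tests are complete. These statements conflict and must be reconciled.

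**The concern.** In a two-period crossover, a shift between first and second test cancels out of the product comparison only if the two orders contribute equally or the analysis accounts for period. The stated estimator does not account for it, and with a third of recruits expected to be lost, equal evaluable sequences cannot be relied on.

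A period shift is possible on the protocol's own terms, because the restrictions on alcohol and non-routine exercise precede only the second test. The primary conclusion is an equivalence claim. A bias towards zero makes false equivalence more likely, and a bias away from zero makes true equivalence harder to show.

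**Working it through.** **Inputs from the protocol (Section 10.2).** One-hour mean 10.6 mmol/L, SD 1.78, margin 20%, N = 28, power 80%, alpha 0.05, loss 33%. The margin is 0.20 × 10.6 = 2.12 mmol/L.

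**Assumptions (not in the protocol).** Pi of 0.5 or 1.0 mmol/L; within-woman correlation 0.5, so the SD of the differences is 1.78 × √(2 × 0.5) = 1.78; alpha 0.05 per side; where stated, 21 women allocated to each order.

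**The plan's own figure.** Two one-sided t-tests on two independent groups, true difference 0, give 80.8% power at 13 per group (N = 26) and 84.5% at 14 per group (N = 28). So 28 roughly matches a calculation for two independent groups. A paired test would need 14 women at correlation 0 and 8 at correlation 0.5. The recruitment target follows: 28/0.67 = 41.8, rounded up to 42.

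**Bias.** Let D be tablets minus beverage, delta the true difference, and n1 and n2 the evaluable beverage-first and tablets-first women. D has mean delta + pi in beverage-first women and delta − pi in tablets-first women. The overall mean of D is therefore biased by pi × (n1 − n2)/(n1 + n2). With complete pairs, the difference of the two product means is the same number and has the same bias.

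| Split of 28 | Factor | Bias, pi 0.5 (share of margin) | Bias, pi 1.0 (share of margin) |
|---|---|---|---|
| 14:14 | 0 | 0 | 0 |
| 16:12 | 4/28 = 0.143 | 0.07 (3.4%) | 0.14 (6.7%) |
| 18:10 | 8/28 = 0.286 | 0.14 (6.7%) | 0.29 (13.5%) |
| 21:7 | 14/28 = 0.5 | 0.25 (11.8%) | 0.50 (23.6%) |

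**How likely is imbalance?** If 14 of 42 (21/21 allocated) are lost at random, the split is hypergeometric. Exact balance has probability 26%, the mean absolute gap is 2.4 women, and a gap of 8 or more has probability 2%. At the mean gap and pi 0.5, the bias is 0.5 × 2.4/28 = 0.04 mmol/L, about 2% of the margin.

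**Variance when balanced.** The period shift enters the spread of D: √(1.78² + 0.5²) = 1.85 and √(1.78² + 1.0²) = 2.04. Simulated paired false equivalence at a true difference of 2.12 then falls to about 4.4% (pi 0.5) and 3.0% (pi 1.0).

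**False equivalence at a true difference of 2.12, nominal 5% (simulation, paired test).**
- Averaged over random splits: about 5.0% at both values of pi under simple 1:1 assignment; with 21/21 allocated and random loss, about 4.7% (pi 0.5) and 3.6% (pi 1.0).
- Given an 18:10 split with bias towards zero: 9.9% and about 15%.
- Given a 21:7 split (all losses in one order) with bias towards zero: 17% and 35%.
- With bias away from zero at either split: below 2%.

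**With period in the model.** Averaging the two sequence means of D gives zero bias at any split, and false equivalence stays at about 5%. The standard error is 0.5 × 1.78 × √(1/n1 + 1/n2): 0.351 at 18:10 and 0.388 at 21:7, against 1.78/√28 = 0.336. Power at zero difference stays above 99%.

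**The case against.** **Random imbalance does not break the test.** A reader might infer from the 18:10 rates that the plan has a 10% to 15% false-equivalence rate. It does not. Those rates are conditional on one unlucky split and one direction of bias; over random splits the paired test stays at or below 5%. This objection stands in full.

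**A split this uneven is rare under random loss.** Under coin-flip assignment of 28 women, 18:10 or worse has an 18% chance, but that models assignment and not loss. Section 5.3.1 describes a prepared table whose balance is not stated. With 21/21 allocated and random loss the chance is about 2%. This also stands.

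**The test is not clearly a paired one.** If two-sample means an unpaired comparison of the products, false equivalence at 18:10 with bias towards zero is 2.9% (pi 0.5) or 6.3% (pi 1.0). The bias itself is unchanged. If it means the textbook crossover test that compares period differences between sequences, the period effect is already removed. Section 10.4 names time points and products but never sequences, so that reading is not established.

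**Pi has no documented size.** The 16.7% in Section 10.4 is within-person variation, not a directional shift. Routine exercise continues and both tests fall within one week, so pi may be small.

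**The statistical analysis plan is not available and may add the term.** That is possible, and the protocol does not say that order will be ignored. But Section 10.4 is headed as the final analysis plan and states an estimator without the term, so its text needs correcting in any case.

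**Conclusion.** The point holds as a modest flaw in the stated primary analysis. The estimator omits the factor that was randomised, and its bias is exactly pi × (n1 − n2)/N. Under random loss the consequence is small: about 0.04 mmol/L on average at an assumed pi of 0.5, with no inflation of the overall false-equivalence rate. Bias alone would reach the 2.12 margin only at a pi of 7.4 mmol/L (18:10) or 4.2 mmol/L (21:7).

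It becomes systematic only if loss depends on order. The protocol makes that possible: a woman who takes the beverage first may already have her diagnostic result and no clinical need for the second visit, whereas a woman who takes the tablets first still needs the beverage test. In the extreme 21:7 case with pi 0.5 and bias towards zero, a paired test would declare false equivalence 17% of the time. The protocol does not show that such loss will occur. The error rates also assume a correlation of 0.5 and a true difference at the margin.

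**What to change.** In Section 10.4 and in the Statistical Analysis row of the Protocol Summary, replace the two-sample comparison with the standard 2×2 crossover analysis: product, period and sequence as fixed effects and woman as a random effect. For complete pairs this is the average of the two sequence-specific mean differences. Base the equivalence decision on the 90% confidence interval for the product difference. If the crossover two-sample test was intended all along, say so and name the sequences.

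The cost is wording, one degree of freedom and a small loss of precision when sequences are unequal (standard error 0.336 to 0.351 at 18:10, assuming correlation 0.5). Sample size and conduct do not change. Separately, reconcile Section 5.3.2 with Sections 4.1 and 6.1.3 on when the beverage result is released, because that timing affects whether loss can depend on order.

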5 PARTICIPANT SELECTION AND WITHDRAWAL

This is a study of diagnostic test validity in pregnant women, so this vulnerable population is the only population that can be studied. Women will be offered enrollment if they fall into the screen positive group after a 50g GCT. Only singleton pregnancies will be included as twin gestations can have higher glucose values and this may impact the generalizability of the results. Women can withdraw from the study at any time, but will be encouraged to complete the standard glucose beverage test as this is the only validated test to provide a diagnosis of GDM at this time. A sample of 28 will provide 80% power at alpha of 0.05 for a test of equivalence with Dex4® tablets assuming a 20% margin of equivalence. The sample size calculation was carried out using PASS Version 12 (Hintze, J. (2014). NCSS, LLC. Kaysville, Utah.) Accounting for loss to follow up of 33%, 42 women will need to be recruited, respectively. Based on data from Alberta, 20% of women screen positive on a 50g GCT (22). Approximately 230 women deliver at Sunnybrook every month, of those 45 will screen positive on the GCT. Assuming a 20% successful recruitment rate we should be able to complete recruitment in 4-6 months. Eligibility criteria must be met by 32 weeks' gestation to allow enrollment in the study.

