6.1.1.2 Packaging

The investigational product is packaged in bottles of 50 tablets each. Participants will be provided with 21 tablets.

6.1.2 *Treatment Assignment Procedures*

All participants will complete both arms of the study (2-hr OGTT with glucose beverage and with Dex4® tablets).

6.1.3 *Dosage, Preparation and Administration*

OGTT testing with both glucose beverage and Dex4® tablets will occur once patients are enrolled. The glucose beverage is the standard of care test and may be performed in the hospital lab by trained phlebotomists. The comparator test with the Dex4® tablets will be performed by a research coordinator with phlebotomy experience or in the hospital lab, depending on availability. Both tests will occur after at least 8 hours fasting, and will require three 2 mL blood samples each, drawn via venipuncture. Results of the glucose beverage test will be recorded in Sunncare and results of OGTT with Dex4® will faxed to the study coordinator with the associated study ID number. Serum glucose results will not be disclosed to the obstetrical care team until both OGTT tests are done. Serum glucose will be measured using the same internationally standardized glucose-oxidase method (Roche Diagnosis) in the Sunnybrook Biochemistry lab. After serum glucose measurement, all results will be sent to the research team but only the glucose beverage OGTT test data will appear in electronic (or classical) medical records.

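### The primary analysis is named as a two-sample equivalence test, which in its ordinary reading ignores the pairing in this crossover and gives an interval of the wrong width unless a woman's two results are uncorrelated

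*Protocol*

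**What the plan says.** Section 4.1 describes the design: "Our project is a population-based, prospective randomized crossover study". It adds: "Each woman will complete both tests within one week and each subject will serve as their own control". Section 6.1.2 repeats that "All participants will complete both arms of the study". Under Section 5.3.1 an allocation table assigns women "to take either the standard OGTT test (75g of glucose beverage) first or the alternative OGTT test (21 Dex4® tablets) first", so there are two randomised sequences.

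For the primary comparison, Section 10.4 calculates "the mean of the differences at each time point" (fasting, 1 hour and 2 hours) and then states that "a two-sample equivalence-test will be used to compare the means". The Statistical Analysis row of the Protocol Summary says the same. Neither place gives a formula, a variance or an interval, or says which two samples are meant. No section names a paired, crossover or between-sequence analysis.

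Section 10.2 says that "a sample of 28 will provide 80% power at alpha of 0.05 for a test of equivalence with Dex4® tablets", using a 1-hour mean of 10.6 mmol/L, an SD of 1.78 mmol/L and a 20% margin. The calculation is repeated in Section 10.4, and its result in the introduction to Section 5. None of these places names the test, says what the SD measures, or gives the true difference assumed.

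**The concern.** The two halves of the analysis sentence point in different directions. A mean of differences is a within-woman quantity. A two-sample test of means, in ordinary use, takes two independent groups and builds its standard error from the two separate variances. This trial has no independent product groups.

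The conclusion on equivalence rests on a confidence interval for the product difference, and the possible readings give different intervals. Ignoring the pairing makes the interval too wide if a woman's two results are positively correlated and too narrow if they are negatively correlated. Two analysts following Section 10.4 in good faith could report different primary results, and the choice would still be open once the data are in hand.

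**Working it through.** **Inputs from Section 10.2:** n = 28 women; 1-hour mean 10.6 and SD 1.78 mmol/L; margin 20%, taken as 0.20 × 10.6 = 2.12 mmol/L; alpha 0.05; power 80%.

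**Assumptions, because the protocol gives no value:**
- The within-woman correlation ρ is -0.3, 0, 0.3, 0.5 or 0.7.
- The SD of 1.78 applies to single values under each product.
- Alpha 0.05 is per one-sided test, which corresponds to a 90% interval.
- There is no period effect, and 14 women follow each order.

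No mean or SD is given for fasting or 2 hours, so only the 1-hour effect can be computed.

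**Step 1: the stated 28.** I used exact power of two one-sided tests (TOST), integrating over the sampling distribution of the SD.
- Independent groups, zero true difference: 13 per group (26 in total) gives 80.8%; 14 per group (28 in total) gives 84.5%.
- Paired, SD of the difference = 1.78 × √(2(1 − ρ)), zero true difference: 14, 10, 8 and 6 women at ρ 0, 0.3, 0.5 and 0.7.
- Paired, true difference 5%: 18, 13, 10 and 7 women.

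The independent-groups reading comes close to 28, but that does not settle the matter. Exactly 28 also results from independent groups with a true 3% difference (28 in total, 80.2%) and from a paired test with ρ 0.25 and a true 10% difference (28 women, 80.6%). The text does not show which test the 28 rests on.

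**Step 2: interval width with 28 women.**
- Two-sample half-width: t(0.95; 54 df) × SD × √(2/28) = 1.674 × 1.78 × 0.267 = 0.796, whatever ρ is.
- Paired half-width: t(0.95; 27 df) × SD × √(2(1 − ρ)/28). At ρ 0.5 this is 1.703 × 1.78 / √28 = 0.573.
- Ratio at ρ 0.5: 0.796 / 0.573 = 1.39.
- Comparison of period differences between sequences (14 v 14, 26 df, t = 1.706): almost the same as paired.

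**Step 3: simulation, 200,000 trials per scenario.** Widths are means in mmol/L. They fall slightly below twice the half-widths above because a sample SD averages a little under its true value.

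| ρ (assumed) | -0.3 | 0 | 0.3 | 0.5 | 0.7 |
|---|---|---|---|---|---|
| 90% interval width, two-sample | 1.58 | 1.58 | 1.58 | 1.58 | 1.58 |
| 90% interval width, paired | 1.83 | 1.61 | 1.34 | 1.14 | 0.88 |
| 90% interval width, sequence comparison | 1.83 | 1.61 | 1.35 | 1.14 | 0.88 |
| False equivalence at a true 20% difference, two-sample | 7.5% | 5.0% | 2.5% | 1.1% | 0.2% |
| False equivalence, paired or sequence | 5% | 5% | 5% | 5% | 5% |
| Power at a true 5% difference, two-sample | 93% | 95% | 98% | 99% | 100% |
| Power at a true 5% difference, paired | 89% | 95% | 99% | 100% | 100% |
| Power at a true 10% difference, two-sample | 69% | 71% | 75% | 78% | 83% |
| Power at a true 10% difference, paired | 60% | 70% | 83% | 92% | 99% |

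At a true 10% difference the sequence comparison lies within 0.1 percentage point of paired.

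**Step 4: the only hint about ρ.** The protocol cites intra-individual variation of up to 16.7%. Read as a within-woman coefficient of variation at 10.6, this gives 0.167 × 10.6 = 1.770 mmol/L, and ρ = 1 − (1.770/1.78)² = 0.01. There the two widths nearly agree. The reading is uncertain: the figure is an upper value, and Section 10.4 ties it to the 2-hour test.

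**The case against.** The strongest reply is that the sentence is unclear rather than wrong. It begins with a mean of differences, which is the paired estimator, and Section 4.1 makes each woman her own control. The term may be a slip for two one-sided tests, or may mean the valid comparison between sequences. A statistical analysis plan could settle the model. The cost also looks small. For ρ of 0 or more, false equivalence does not exceed 5%, and power at a true difference of 0 or 5% is about 95% or higher. Nothing suggests that two glucose tests in one woman within a week would be negatively correlated, and the 16.7% figure may even point to ρ near zero.

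Much of this stands and limits the weight of the point: the size of the effect is uncertain, and its likely direction is conservative. Whether the crossover model includes a period term can indeed be left to an analysis plan. But the protocol does not leave the primary test open. It names one in two places, and the ordinary meaning of that name does not fit the design. The readings that would rescue it are not written down, and the sample size does not reveal which was intended.

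**Conclusion.** The point holds: the primary test is wrongly named for this design and should be corrected. It does not undermine the trial. At the 1-hour planning values the two-sample interval is about right at ρ 0, 39% too wide at ρ 0.5, and too narrow if ρ is negative. A material loss of power appears only near a true difference of 10% with ρ of about 0.3 or more (75% v 83% at 0.3, 78% v 92% at 0.5). False equivalence rises above 5% only with negative correlation (7.5% at ρ -0.3).

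Confidence is high that the named test does not match the crossover in its ordinary reading and that the sequence reading is not described. It is low on the size of the effect, which depends on a correlation the protocol does not give and on the assumptions listed above. The effect at fasting and 2 hours cannot be computed.

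**What to change.** - **Section 10.4 and the Protocol Summary:** replace the two-sample test with a within-woman equivalence analysis, either a paired TOST or a crossover analysis with product and period that uses the randomised order. If the comparison of period differences between sequences was meant, say so.
- **Decision rule:** judge equivalence by the confidence interval for Dex4 minus beverage against the 20% margin. This is the 90% interval if alpha 0.05 is meant per one-sided test; state which is meant.
- **Section 10.2, its repeat in 10.4, and the Section 5 introduction:** name the same test for the sample size. State whether 1.78 is the SD of single values or of within-woman differences, and what true difference was assumed.

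The cost is wording plus a restated sample-size calculation, with no new data. With ρ of 0 or more, 28 completers exceed the paired requirement at a true difference of 0 or 5% (at most 18 women). If the sponsor wants 80% power at a true 10% difference, a paired TOST needs 37 women at ρ 0 and 26 at ρ 0.3. The restated calculation should therefore be explicit on that assumption.
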